3.3 Early Withdrawal of Subjects

3.3.1 Criteria for removal from study

Insert subject withdrawal criteria (e.g., safety reasons, failure of subject to adhere to protocol requirements, subject consent withdrawal, disease progression, etc.).

- New need for medical hospitalization for malnutrition or eating disorder
- Need for escalation of level of care for eating disorder, that is, requirement for inpatient or residential-level eating disorder care
- New need for opioid painkillers
- Subject consent withdrawal
- Inability to adhere to protocol requirements
- New diagnosis of pregnancy
- New elevation of three times the upper limit of normal for age in either alanine aminotransferase (ALT) or asparagine aminotransferase (AST).

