3.3.2 Follow-up for withdrawn subjects

Describe when and how to withdraw subjects from the study; the type and timing of the data to be collected for withdrawal of subjects; whether and how subjects are to be replaced; the follow-up for subjects withdrawn from investigational treatment.

- Patients who are withdrawn from the study will continue with their routine eating disorder
 care at whatever level of care is clinically appropriate for them at that time; that is, they will
 continue with routine care. Data generated from their participation in this study will be used
 to the point of their withdrawal. Specific study subjects do not require replacement.
- Patients who screen positive for opioid substances at enrollment will be provided with a referral for substance use disorder treatment.
- Patients who screen positive for pregnancy will be referred for pregnancy options counseling.

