7.3.2 Treatment Regimen

Describe dose, route of administration and treatment duration. Include information about dose adjustments.

All subjects receiving study medication will receive oral naltrexone 50mg oral tablets, blinded as described above. All subjects receiving placebo will receive methylcellulose, blinded as described above. All capsules, regardless of contents, will be administered by mouth once daily, at a time of day to be chosen by the study participant.

In pediatric autism literature, doses between 0.5-2 mg/kg are described^{8,11,22,22-25}, though in adult eating disorder literature doses of 50-100mg are described^{13,14,16-18}. Food and Drug Administration labelling of oral naltrexone for treatment of alcohol use disorder and opioid receptor blockade describe an appropriate maintenance dose of 50mg per day⁷. Therefore subjects will receive 50mg of oral naltrexone a day if they are randomized to the medication group. Patients with body weight less than 25kg are excluded from the study so that no participant will exceed the maximum described pediatric dose of 2 mg/kg. Participants receiving

study article will receive 25mg of naltrexone for three days, followed by increase to study dose of 50mg/day The maximum daily dose is 50mg.

Participants will take study medication daily while they are in PHP or for six weeks total. That is, if a participant is in PHP for three weeks, they will take the study medication for the entirety of their time in PHP and then continue to take the medication for three additional weeks after discharge from PHP. If a participant is in PHP for twelve weeks—which is quite uncommon—they will only take study medication for six weeks.

For participants who complete PHP early, they will be asked to complete the same battery of surveys at 3 and 6 weeks, at weeks 8/9 for post-treatment evaluation, and at 6 months. Survey responses will be obtained via RedCAP for participants not on-site at time of survey completion.

Participants who, upon completion of the study, feel that they had significant benefit from the study article which lost upon withdrawal of the study article, are eligible for open label oral naltrexone therapy if desired. Participants will be asked at subsequent medical and behavioral health follow-up appointments if they felt they benefitted from the study article. If they feel they did, they will be offered a prescription for oral naltrexone to start at 25mg/day for three days and then 50mg a day after.

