Should any participant demonstrate elevation of AST/ALT above the upper limit of normal for age, the study article will be discontinued. AST and ALT measures will be obtained twice weekly until they have normalized. More complete history will be obtained, specifically with respect to medications, supplements, recreational drug use history, travel, and chemical exposure. Participants with elevation of AST and ALT will also be evaluated for acute viral hepatitis types A, B, C, D, and E; autoimmune hepatitis, alcoholic hepatitis, non-alcoholic steatohepatitis, biliary tract disease, and hypoxic/ischemic hepatopathy. The liver's function will be assessed directly via measurement of direct bilirubin and nternational normalised ratio (INR).

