10.0 Risks

List the reasonably foreseeable risks, discomforts, hazards, or inconveniences to the subjects related the subjects' participation in the research. Include as may be useful for the IRB's consideration, a description of the probability, magnitude, duration and reversibility of the risks. Consider all types of risk including physical, psychological, social, legal, and economic risks. Note: Loss of confidentiality is a potential risk when conducting human subject research.

- If applicable, indicate which procedures may have risks to the subjects that are currently unforeseeable.
- If applicable, indicate which procedures may have risks to an embryo or fetus should the subject be or become pregnant.
- If applicable, describe risks to others who are not subjects.

Risks associated with taking oral naltrexone:

- elevated transaminases
- depression and mood changes
- abdominal pain
- nausea
- headache

Additional clinical risks that could be associated with taking Oral Naltrexone:

- Some pediatric autism literature describes low appetite or occasionally worsening of self-injurious behavior while on naltrexone^{8,11,22,22–25,27}. There can also be worsening depression according to the FDA label⁷. These adverse effects are occasionally seen with PHP for eating disorder itself, and therefore we monitor for them frequently as a part of the standard of care. Should the subject or the subject's parent wish to withdraw from the study due to these effects, they are free to do so. If these adverse effects are felt to be related more to the natural history of eating disorder and not to study intervention; or the severity is minor to moderate; the subject may continue to participate in the study if desired. If the effect is severe the subject will be withdrawn.
- Oral naltrexone is a pregnancy category C medication⁷, where there are animal studies that may indicate
 harm to the fetus but no specific human studies on this topic. For this reason, we will test for pregnancy
 in allbirth-assigned females at enrollment using a serum pregnancy screen, and every three weeks
 throughout the study using a urine pregnancy screen. The majority of patients enrolled in child PHP
 have not yet had coitarche, though in adult PHP a history of sexual activity is more common.

Other risks of participation include:

- Loss of confidentiality
- Risk of randomization
- Risk of incidental findings
 Anxiety from completing questionnaires

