18.2 Recording of Adverse Events

Address the frequency and process for eliciting adverse event information from research subject, e.g., "Research subjects will be routinely questioned about adverse events at study visits."

In the response, incorporate the following as written:

All adverse events (serious or non-serious) and abnormal test findings observed or reported to study team believed to be associated with the study drug(s) or device(s) will be followed until the event (or its sequelae) or the abnormal test finding resolves or stabilizes at a level acceptable to the investigator.

An abnormal test finding will be classified as an adverse event if one or more of the following criteria are met:

- The test finding is accompanied by clinical symptoms
- The test finding necessitates additional diagnostic evaluation(s) or medical/surgical intervention; including significant additional concomitant drug treatment or other therapy **NOTE:** Simply repeating a test finding, in the absence of any of the other listed criteria, does not constitute an adverse event.
- The test finding leads to a change in study drug dosing or discontinuation of subject participation in the clinical research study
- The test finding is considered an adverse event by the investigator.

Research subjects will be routinely questioned about adverse events at both study visits and routine care for PHP.

All adverse events (serious or non-serious) and abnormal test findings observed or reported to study team believed to be associated with the study drug(s) or device(s) will be followed until the event (or its sequelae) or the abnormal test finding resolves or stabilizes at a level acceptable to the investigator.

An abnormal test finding will be classified as an adverse event if one or more of the following criteria are met:

- The test finding is accompanied by clinical symptoms
- The test finding necessitates additional diagnostic evaluation(s) or medical/surgical intervention; including significant additional concomitant drug treatment or other therapy
 NOTE: Simply repeating a test finding, in the absence of any of the other listed criteria, does not constitute an adverse event.
- The test finding leads to a change in study drug dosing or discontinuation of subject participation in the clinical research study

• The test finding is considered an adverse event by the investigator.

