18.5 Reporting Adverse Reactions and Unanticipated Problems to the Responsible IRB

By submitting this study for review, you agree to the following statement – DO NOT ALTER OR DELETE:

In accordance with applicable policies of The Pennsylvania State University Institutional Review Board (IRB), the investigator will report, to the IRB, any observed or reported harm (adverse event) experienced by a subject or other individual, which in the opinion of the investigator is determined to be (1) unexpected; and (2) probably related to the research procedures. Harms (adverse events) will be submitted to the IRB in accordance with the IRB policies and procedures.

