19.1.2 Safety Monitoring

Include this section if FDA regulations apply to this study (see "WORKSHEET: Drugs (HRP-306)" and "WORKSHEET: Devices (HRP-307)". HRP-306 and HRP-307 can be accessed by clicking the Library link in CATS IRB (http://irb.psu.edu).

Indicate the process for identifying, recording and reporting adverse events.

Specify roles for adverse event recording and monitoring. Indicate each staff member's role in the adverse event reporting process. Include the following if applicable:

The **Principal Investigator** will confirm that all adverse events (AE) are correctly entered into the AE case report forms by the coordinator; be available to answer any questions that the coordinators may have concerning AEs; and will notify the IRB, FDA, sponsor and/or DSMB of all applicable AEs as appropriate. All assessments of AEs will be made by a licensed medical professional who is an investigator on the research.

The **Research Coordinator** will complete the appropriate report form and logs; assist the PI to prepare reports and notify the IRB, FDA and/or DSMB of all Unanticipated Problems/SAE's.

The **Monitor** will confirm that the AEs are correctly entered into the case report forms. The Monitor will also confirm that the adverse events are consistent with the source documents and are reported to the appropriate regulatory bodies as required.

The principal investigator assumes final responsibility for monitoring the safety of this study. Monitoring for adverse effects to medication will occur at all biweekly medical appointments as a part of routine care during PHP. If a participant develops any observable harm that is probably related to the study articles or materials the participant will be withdrawn from the study and adverse event reporting per IRB protocol will be performed.

The Principal Investigator will confirm that all adverse events (AE) are correctly entered into the AE case report forms by the coordinator; be available to answer any questions that the coordinators may have concerning AEs; and will notify the IRB, FDA, sponsor and/or DSMB of all applicable AEs as appropriate. All assessments of AEs will be made by a licensed medical professional who is an investigator on the research.

The Research Coordinator will complete the appropriate report form and logs; assist the PI to prepare reports and notify the IRB, FDA of all Unanticipated Problems/SAE's.

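### For minor-to-moderate low appetite, self-injury or depression judged probably drug-related, section 10.0 permits continuation while 19.1.2 requires withdrawal; after withdrawal, 3.3.2 makes no use of later ED-15 scores

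*Combined protocol and SAP*

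**What the plan says.** **Two rules for adverse effects.** Section 10.0 Risks names low appetite, worsening self-injury and worsening depression as possible effects of naltrexone. If they seem to come more from the eating disorder than from the intervention, "or the severity is minor to moderate; the subject may continue to participate in the study if desired". Severe effects lead to withdrawal. Section 19.1.2 Safety Monitoring has no severity limit: with "any observable harm that is probably related to the study articles or materials the participant will be withdrawn from the study".

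**The removal list.** Section 3.3.1 gives seven criteria. One is ALT or AST at three times the upper limit of normal. None is a general adverse-event criterion.

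**After withdrawal.** Section 3.3.2 sends withdrawn participants back to routine care and uses their data "to the point of their withdrawal". Section 13.0 withholds the 6-month $25 payment after withdrawal for any reason. Safety follow-up does go on: under 18.2, adverse events believed to be drug-associated "will be followed until the event (or its sequelae) or the abnormal test finding resolves or stabilizes at a level acceptable to the investigator".

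**Stopping drug as a separate step.** Sections 9.8 and 18.7 both state: "Should any participant demonstrate elevation of AST/ALT above the upper limit of normal for age, the study article will be discontinued". Neither says whether surveys continue afterwards.

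**Survey routes.** Section 7.3.2 provides: "Survey responses will be obtained via RedCAP for participants not on-site at time of survey completion". Section 7.2 Study Procedures makes the ED-15 routine care every 3 weeks in the adult program. The child program routinely uses a different inventory, so there the ED-15 is completed because of the study.

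**The concern.** Clinic staff have two instructions for the same event. A participant with moderate low mood judged probably due to naltrexone may stay if she wishes under 10.0 and must leave under 19.1.2. Following either section departs from the other. The three effects are foreseeable: 10.0 lists them as drug risks and says they are occasionally seen with the partial hospitalization program (PHP) itself.

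The choice also affects the data. Withdrawal from the study, as opposed to stopping study article, ends the use of that participant's ED-15 scores. Because the trigger is suspected drug harm, the losses may differ by arm. Section 8.3 compares arms at 3 and 6 weeks and at 6 months, and states neither an analysis set nor a method for missing scores.

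**Working it through.** **Step 1. Set the two rules side by side, for the three effects named in 10.0.**

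| Effect judged to be | 10.0 | 19.1.2 | Agree? |
|---|---|---|---|
| Severe, probably drug-related | Withdraw | Withdraw | Yes |
| Minor to moderate, probably drug-related | May continue | Withdraw | **No** |
| Minor to moderate, more disease-related | May continue | Not triggered | Yes |

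The conflict sits in the middle row. It arises because 10.0 joins its two conditions with 'or', so mild or moderate severity is enough by itself to permit continuation.

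**Step 2. Look for a text that settles it.** Section 3.3.1 is silent. Section 19.1.2 cannot be narrowed to unexpected harms: that qualifier belongs to the IRB reporting rule in 18.5, which covers events "determined to be (1) unexpected; and (2) probably related to the research procedures". The withdrawal sentence does not carry it.

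**Step 3. What happens to ED-15 scores after withdrawal.**

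| Setting | Scores after withdrawal |
|---|---|
| Adult program, still attending | Exist as routine care every 3 weeks, but are not used |
| Child program | No collection provided for |
| After discharge from either program | No collection provided for |
| Weeks 8/9 and month 6 | No collection provided for |

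**Step 4. Illustrate the size.** The plan has no power, effect-size, SD or dropout figure to reproduce; 8.1 and 8.2 set 30 per arm on feasibility. Assumptions: SD = 1; a share pN of the naltrexone arm and pP of the placebo arm withdrawn for adverse effects before the endpoint; those withdrawn would have scored 0.5 SD worse than those remaining; two-sided 5% test. The rates cover all adverse-effect withdrawals, so they overstate the disputed row.

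- Shift among those remaining = 0.5 × (pN − pP); positive favours naltrexone.
- SE = √[1/(30(1 − pN)) + 1/(30(1 − pP))].
- Type I error: normal approximation with the mean shifted by shift/SE.
- Power: two-sample t test, true difference 0.5 SD.

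| pN / pP | Shift (SD) | SE (SD) | Type I error | Power |
|---|---|---|---|---|
| 0 / 0 | 0 | 0.258 | 5.0% | 47.8% |
| 5% / 5% | 0 | 0.265 | 5.0% | 45.8% |
| 5% / 10% | −0.025 | 0.269 | 5.1% | 44.8% |
| 10% / 5% | +0.025 | 0.269 | 5.1% | 44.8% |
| 10% / 10% | 0 | 0.272 | 5.0% | 43.8% |
| 20% / 5% | +0.075 | 0.277 | 5.8% | 42.5% |
| 20% / 10% | +0.050 | 0.281 | 5.4% | 41.6% |

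If those withdrawn would have scored better, the shifts change sign.

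**Step 5. Does keeping the scores raise power?** With everyone followed, n stays at 30 v 30, but the comparison includes time off drug. If the effect disappears on stopping:

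- 10% of the naltrexone arm stop: 0.90 × 0.5 = 0.45 SD, power 40%, against 44–45% among those remaining.
- 20% stop: 0.80 × 0.5 = 0.40 SD, power 33%, against about 42%.
- 20% stop and half the effect persists: 0.80 × 0.5 + 0.20 × 0.25 = 0.45 SD, power 40%.

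If the full effect persisted, power would return to 47.8%. The direction depends on persistence, which the documents do not give.

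**The case against.** The strongest reply is that the conflict is narrow. It concerns three effects, at minor or moderate severity, and only when judged probably drug-related. Section 9.8 says worsening depression and self-injury are also features of the disease or its treatment, so that judgement may often not be reached, and it is made blinded. Section 10.0 could be read as the specific rule and 19.1.2 as the general one, and one clarifying sentence would settle it. All this is fair as to scope. But neither section says it yields to the other, so staff still lack an instruction.

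A reader might infer that withdrawal stops ED-15 collection altogether. The documents do not support that. Section 3.3.2 limits the use of data, and adult-program patients go on completing the ED-15 while they attend; 7.2 Duration of Participation puts the average PHP stay at about 8 weeks. For many of them, scores near weeks 3 and 6 would exist. The gap in collection is confined to the other settings in Step 3.

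A reader might also infer that retaining scores restores power. Step 5 shows it can lower it. As-randomised follow-up answers a question about assignment, including time off drug; the reason to prefer it is that it keeps the randomised groups together.

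Finally, one might adopt the 10.0 threshold for every harm. That section was written for three effects. Extending it would loosen the rule for all other probable drug harms in a trial that enrols from age 13, and would clash with the rule stopping study article for any AST or ALT above normal.

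**Conclusion.** The contradiction between 10.0 and 19.1.2 is established by the text, for minor-to-moderate low appetite, worsening self-injury or worsening depression judged probably drug-related, and no other section resolves it. That withdrawn participants' later scores go unused is also established; that they go uncollected holds only in the child program, after discharge, and at weeks 8/9 and month 6.

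The statistical consequence is unknown in size and direction and probably small. Under the assumptions of Step 4 the shift does not exceed 0.075 SD in either direction, and type I error stays between 5.0% and 5.8%. Those rates and the 0.5 SD gap are not in the documents. The trial is a pilot with no power target, and no power gain is claimed. The case for changing the text is that staff need one rule and that outcome scores can be kept at little cost.

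**What to change.** 1. In 3.3.2, 10.0 and 19.1.2, make the consequence of an adverse effect that study article is stopped, not that the participant is withdrawn from the study.
2. Unless consent is withdrawn, keep collecting and using the ED-15 and other surveys at whichever of weeks 3, 6, 8/9 and month 6 remain, by REDCap or in person. Keep the 6-month payment, amending 13.0 to match, and analyse participants as randomised.
3. Apply the same follow-up to participants who stop under the AST/ALT rules in 3.3.1, 9.8 and 18.7. Leave those thresholds unchanged.
4. State one rule in 3.3.1, 10.0 and 19.1.2. The sponsor decides on clinical grounds whether 10.0 is an exception to 19.1.2 for its three named effects only. Until then the stricter 19.1.2 rule applies: stop study article for any probably related harm. All other harms stay under 19.1.2.

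**Cost.** Protocol wording and a little more follow-up work through a REDCap route already in use. Retained payments under the assumed rates are (1.5 + 1.5) × $25 = $75 to (6 + 3) × $25 = $225. The main downside is that the comparison will include time off drug, which may dilute the estimated effect; the analysis section should say so.

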11.0 Potential Benefits to Subjects and Others

11.1 Potential Benefits to Subjects

Describe the potential benefits that individual subjects may experience from taking part in the research. If there is no direct benefit to subjects, indicate as such. Compensation is not considered a benefit. Compensation should be addressed in section 14.0.

There is potential direct benefit to participants, as the study intervention may improve eating disorder symptoms more rapidly than PHP alone.

Participants receiving placebo are not expected to have direct benefit.

11.2 Potential Benefits to Others

Include benefits to society or others.

Others may potentially benefit if oral naltrexone is shown to have some efficacy over PHP alone, as there are not many effective pharmacotherapies for eating disorder. If this medication is shown to have some beneficial effect in this study, the hope is that eating disorder may have another treatment option.

12.0 Sharing Results with Subjects

Describe whether results (study results or individual subject results, such as results of investigational diagnostic tests, genetic tests, or incidental findings) will be shared with subjects or others (e.g., the subject's primary care physicians) and if so, describe how information will be shared.

Any information collected as a part of standard of care will be shared with the participant and the participant's primary care provider as it would have otherwise been shared with them during PHP, usually in weekly-to-monthly letters to the primary care provider or via patient portal. This includes lab results and survey results. Any additional information obtained, such as ABUSI results or liver function tests at 6 weeks, may be shared in the same fashion.

